This study is designed to generate level 1 evidence of diagnostic effectiveness

For both protocols, screen positive and screen negative results are based on the antenatal detection of a small for gestational age (SGA) neonate namely a newborn with a birth weight $<10^{\text{th}}$ centile.

MAIN OUTCOME

The main outcome of the two protocols in screening late preterm and term SGA fetuses at term is measured based Intergrowth21th newborn weight charts centiles $<\text{the } 10^{\text{th}}$ according to gender.

SECONDARY OUTCOME

1. Mode of delivery
2. Caesarean section rate
3. Composite mild adverse neonatal outcome (Apgar score at 5 minutes <7 , pH < 7.10 , or BD $>8\text{mmol/L}$, admission at NICU)
4. Composite severe adverse perinatal (stillbirth or term live birth associated with neonatal death, hypoxic ischaemic encephalopathy, use of inotropes, need for mechanical ventilation, or severe metabolic acidosis (defined as a cord blood pH <7.0 and base deficit $>12 \text{ mmol/L}$).

TERTIARY OUTCOME

1. Econometrics of the two protocols, and of the estimated sanitary costs of outcomes

EXPECTED RESULTS

We hypothesize that the Longitudinal Scan Protocol with a 28-32 AND a 35-37 weeks universal screening will outperform the Single scan Protocol for the primary outcome regarding the detection Rate of IUGR. On the other hand, as this Protocol will be the more expensive one, we hypothesize that the most cost effective protocol will be the universal single late scan at 35-37 weeks of gestation so underlying the clinical utility of a late single scan for the low risk population.

The secondary outcomes are subjected to local protocols and we should expect a reduction of the composite neonatal adverse outcome in the late single scan protocol and in the longitudinal one. Last but not least, we hypothesize that the inferred Econometrics of the two protocols will provide evidence of the reduced health care costs of the universal screening when properly based on biological and clinical data obtained by this branch of medicine in recent years (R.P.) versus old tenets of the early years of the introduction of ultrasound in obstetrics (I.P.).

STATISTICS

Sample size is based on sensitivity in detecting SGA below 10th centile weight at birth. For the 28-32 group, sensitivity is based on results by Roma et al. (22.5%). The results published by Sovio et al. are instead taken for the “longitudinal” group (57% sensitivity).

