The sample size calculations have been carried out for the comparison between the 28-32 only group vs. the “longitudinal”. Calculations considered a confidence level of 95% (1-alpha) and an 80% power (1-beta), and a one to one ratio between the 28-32 only groups and the “longitudinal”. According to Fleiss (Fleiss JL. Statistical methods for rates and proportions, II Ed. John Wiley & Sons, New York, 1981. page 45, formulas 3.18 & 3.19), for the 28-32 group vs. the “longitudinal”, each arm should comprise 32 subjects, which implies 64 for two arms. The sample size needed considering both AGA and SGA, will then be $64 \times 10 = 640$. Considering 10% of drop-out and incomplete data the final sample size should be increased of such percentage, reaching 704 subjects.

The sample should be recruited according to the number of deliveries per year of each institute involved in the multicenter study. Analysis will be based on intention to treat. Demographic and maternal characteristics variables will be collected in order to describe the population of women recruited in the study and reassure about the result of randomization

A Kolmogorov-Smirnov or Shapiro-Wilk test and visual plot inspection will be used to assess normality of arithmetic data distributions. Parametric or non-parametric tests will be used to compare variables between the groups, and comparison of proportions will be performed using Chi-square or Fisher’s exact test, as appropriate.

Logistic regression models will be used to determine the magnitude of the association between ultrasound variables and newborn’s weight $<10^{\circ}$ centile and neonatal outcome.

Performance of Single Scan and Longitudinal Scan screening policy in identifying late preterm and term SGA will be calculated and compared between arms. The area under the receiver operating characteristic (ROC) curve will be estimated with 95% confidence intervals. Next, the screening performance will be then summarized in terms of sensitivity, specificity, positive and negative predictive values and likelihood ratios.

A p value <0.05 will be considered statistically significant.

Figure 1 : Flow chart of the randomized trial

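### The 10% allowance for loss is applied as × 1.10, so 704 women leave about 634 for analysis, not the 640 the plan says it needs

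*Combined protocol and SAP*

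**What the plan says.** The sample-size paragraphs of STATISTICS proceed in three steps.

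1. Sensitivities of 22.5% (single scan at 28-32 weeks) and 57% (longitudinal) are compared at 95% confidence with 80% power and 1:1 allocation. Since sensitivity is measured only in SGA newborns, the result is a count of SGA cases: "each arm should comprise 32 subjects, which implies 64 for two arms".
2. That count is scaled to all women: "The sample size needed considering both AGA and SGA, will then be" 64 × 10 = 640. The multiplier of 10 implies an SGA prevalence of 10%.
3. The plan expects 10% drop-out and incomplete data and enlarges the total by that percentage: "the final sample size should be increased of such percentage, reaching 704 subjects".

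No other section gives a different recruitment target or says how many women should remain for analysis.

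**The concern.** The 640 is the number needed to obtain 64 SGA newborns with usable data, and the 704 is the number to recruit. Drop-out and incomplete data arise among the women recruited, so the 10% has to be taken from 704. Adding 10% to 640 and then losing 10% of the larger total does not return to 640.

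At stake is whether the headline target delivers the requirement it was built from. A reader will take 704 to mean that 640 women and 64 SGA births remain if the plan's own loss rate is met. They do not, even if every assumption holds exactly.

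**Working it through.** **Inputs, all from STATISTICS:** sensitivities 0.225 and 0.57; 95% confidence and 80% power; 1:1 allocation; 32 SGA cases per arm; multiplier 10; loss 10%; final size 704. The sidedness of the calculation is not stated; two-sided is assumed here.

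**Step 1: the base figure.** The usual formula for two proportions, with pooled variance under the null and no continuity correction, is

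n = [1.96 × √(2p̄(1 − p̄)) + 0.8416 × √(p₁(1 − p₁) + p₂(1 − p₂))]² / (p₁ − p₂)²

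with p̄ = (0.225 + 0.57) / 2 = 0.3975. The two square roots are 0.6921 and 0.6477, and the difference is 0.345, so

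n = (1.96 × 0.6921 + 0.8416 × 0.6477)² / 0.345² = 30.4, rounded up to 31 per arm.

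The plan's 32 is one more than this. The plan's 32 is used from here on.

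**Step 2: the plan's totals.** 32 × 2 = 64; 64 × 10 = 640; 640 × 1.10 = 704. The stated figure is reproduced exactly, so the allowance was applied as n × (1 + d).

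**Step 3: what 704 delivers at the plan's loss rate.**

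| Quantity | Plan's requirement | From 704 with 10% loss |
|---|---|---|
| Women for analysis | 640 | 704 × 0.90 = 633.6 |
| SGA births at 10% | 64 | 63.4 |
| SGA births per arm | 32 | 31.7 |

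The shortfall is 640 − 633.6 = 6.4 women, or about 0.64 of an SGA birth.

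**Step 4: the size that keeps 640.** n / (1 − d) = 640 / 0.90 = 711.1, rounded up to 712 (356 per arm), which is 8 more than 704. Conversely, 704 keeps 640 only if the loss is at most 1 − 640/704 = 9.1%.

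**Step 5: effect on power** (two-sided 5%, no continuity correction).

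| Basis | At 640 women | At about 634 women |
|---|---|---|
| Normal approximation, SGA count fixed at its expected value (32 or 31.7 per arm) | 82.1% | 81.7% |
| Exact power of the chi-square test, averaged over binomial SGA counts (320 or 317 women per arm) | 81.7% | 81.3% |

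Either way the loss is about 0.4 percentage points.

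**The case against.** The strongest reply is that the plan makes no slip on its own terms. It says the total is increased by 10%, and 640 increased by 10% is 704. It never states that 704 less 10% leaves 640, and it does not use the word evaluable. On this view the issue is a choice of inflation method that covers a 9.1% loss, and 10% is a round figure given without a source, so the distinction is finer than the assumption supports.

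The reply adds that nothing is lost in practice. On the uncorrected formula 30.4 SGA cases per arm suffice for 80% power, and 31.7 exceeds that. The SGA count is also random: with 640 women at 10% prevalence its standard deviation is √(640 × 0.10 × 0.90) = 7.6 births. The chance of reaching at least 64 is about 52% with 640 women and about 49% with 634, so enrolling 712 would not secure 64 births either. In addition, the Study protocol section excludes women with abnormal abdominal circumference or fetal weight at 19-21 weeks, and those with suspected anomalies, without saying whether the 10% covers them. That uncertainty could exceed 8 women.

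Most of this stands, and it settles the size of the point. The multiplication is correct as a multiplication, and 80% power is still met on the uncorrected formula. What does not stand is that there is nothing to correct. The plan calls 640 the size needed and names 10% as the loss to allow for; at that rate 704 leaves fewer than 640. The doubt about exclusions is a further reason to state plainly what 704 yields.

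**Conclusion.** The point holds. With 10% loss, 704 women leave about 634 for analysis and about 63 SGA births, against the 640 and 64 the plan sets as its need. The arithmetic needs no outside assumption: the loss rate, the SGA ratio and both totals are the plan's own.

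It is minor: 6 women for analysis, 8 enrolled, and about 0.4 percentage points of power. The statement that power stays above 80% assumes a two-sided test without continuity correction and the plan's sensitivities and prevalence. With a two-sided continuity correction 36 SGA cases per arm would be needed, and power is already about 74% at 32 per arm and about 73.5% at 31.7. The documents do not show which version of the cited formulas was used. On either basis the inflation step is not what decides adequacy.

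**What to change.** Amend the last step of the sample-size paragraph in STATISTICS to say what 704 provides: with 10% drop-out and incomplete data, about 634 women and about 63 SGA births (31.7 per arm), with power quoted at that size and the test and sidedness named. The same sentence can say that 704 retains 640 women only if loss does not exceed 9.1%. This changes one sentence, adds no women and leaves the design untouched.

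Alternatively, set the target at 640 / 0.90 = 712, at a cost of 8 more women. The restatement is sufficient; the gain in power is too small to require the extra recruitment. In either case, add whether the 10% is meant to include the exclusions made after recruitment, so that the allowance can be checked against actual losses.

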Eligible cases are **nulliparous pregnant women**, with first trimester ultrasound assessment of gestational age, **who conceived singleton fetuses**. If the crown-rump-length (CRL) differs of more than $\pm 3-5$ days from the last menstrual period, gestational age is calculated on the CRL. Women who agree to participate are randomized to the Single scan protocol or Longitudinal scan protocol. In practical terms this means that in each participating centre the randomization will be on two arms but the time of the single scan assessment will be dependent on the Regional Health Authority regulation (LEA: Livelli Essenziali di Assistenza)

Exclusion criteria:

- major medical disease
- pregnancy conceived by IVF/ICSI
- known immune disorders or clinical thrombophilic conditions;
- twin pregnancies;
- high risk for preeclampsia detected in those centres that perform pre-eclampsia screening at first trimester
- Papp-A at Combined-Test<0.2

Study protocol:

Eligibility check, information on this trial, offer to be recruited will be performed by the local investigator at the 19-21 weeks of gestation scan.

Women who agree to take part into the trial and sign an informed consent, will be randomized **to the Single Scan Protocol (28-32 weeks scan) or to the Longitudinal Scan Protocol (scan both at 28-32 AND 35-37 weeks)**. Demographic characteristics and medical history of recruited women are recorded on the CRF. The same demographic and clinical data of eligible women who refuses to be recruited will be recorded for analysis between trial cohort and eligible non recruited women. To define fetal growth disorders we will adopt the Delphi criteria for the diagnosis of IUGR.

Women randomized to the **Single scan Protocol** will receive the standard package of sonographic anatomy and biometric screening offered by the Regional Health Service at 19-21 weeks of gestation and biometric screening at 28-32.

- **Single Scan protocol at 19-21 weeks:** if **AC biometry and/or fetal weight are normal** a biometric scan is scheduled basing on the regional LEA at 28-32 weeks of gestation .If **AC biometry and/or fetal weight are abnormal the case is excluded** from further analysis for third trimester screening, and the patient is then monitored according to local protocol.

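### Unadjusted arm comparisons of caesarean section and the neonatal composites are valid but give up a modest amount of precision that pre-randomisation maternal data could supply

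*Combined protocol and SAP*

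**What the plan says.** Under STUDY DESIGN, Study protocol: "Demographic characteristics and medical history of recruited women are recorded on the CRF". The documents name three uses for these data:

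- describing the cohort (STATISTICS: "Demographic and maternal characteristics variables will be collected in order to describe the population of women recruited in the study");
- giving reassurance that randomisation worked (same sentence);
- comparing recruited women with eligible women who decline (Study protocol).

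For between-arm tests, STATISTICS states that "comparison of proportions will be performed using Chi-square or Fisher" exact test, with parametric or non-parametric tests for other variables. The one regression in the plan is logistic. It relates ultrasound variables to birth weight below the 10th centile and to neonatal outcome, with no arm term and no maternal covariate named. It is therefore an association model and not an adjusted comparison of the arms.

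SECONDARY OUTCOME lists mode of delivery, caesarean rate, and a mild and a severe composite. No expected rate is given for any of them. EXPECTED RESULTS anticipates a fall in the composite neonatal outcome and says that the secondary outcomes depend on local protocols. Inclusion criteria describes two-arm randomisation in each participating centre.

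**The concern.** The sample size rests on sensitivity alone. The secondary outcomes have no power statement, yet the sponsor expects a benefit on the neonatal composite. These comparisons will rest on about 320 evaluable women per arm.

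If some recorded maternal variables predict caesarean section or neonatal outcome, leaving them out makes the confidence intervals wider than they need be. The plan also intends to inspect baseline balance but gives no rule for what follows if an imbalance appears. That leaves room to choose covariates after seeing the data. What is at stake is the width of secondary intervals and the discipline of any later adjustment.

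**Working it through.** **Inputs from STATISTICS.** Sensitivity 22.5% versus 57% (the latter given as "57% sensitivity"), 95% confidence, 80% power, 1:1 allocation. The stated result is "each arm should comprise 32 subjects, which implies 64 for two arms", then 64 × 10 = 640, and 704 after a 10% allowance. Sidedness is not stated; two-sided is assumed.

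**Step 1: the plan's own figure.** Pooled formula without continuity correction:

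n = [z₀.₉₇₅√(2p̄(1−p̄)) + z₀.₈₀√(p₁(1−p₁) + p₂(1−p₂))]² / (p₂−p₁)²

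With p̄ = (0.225 + 0.57)/2 = 0.3975 and p₂−p₁ = 0.345, this gives 30.4, rounded up to 31, against the stated 32. With continuity correction it gives 36. At 32 per arm, power is 82.1% by the uncorrected formula. 640 × 1.10 = 704 and 640/2 = 320 per arm. The plan's figure is reproduced closely enough, and nothing below alters it.

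**Step 2: variance gain from adjustment.** With 1:1 allocation, the large-sample variance of the covariate-adjusted marginal risk difference is about (1−R²) times the unadjusted variance. Here R² = Var(E[Y|X])/Var(Y). The effective number per arm is 320/(1−R²). Event rates and covariate strength (AUC 0.60 to 0.75) are assumptions. Power is for an assumed one-third relative reduction, two-sided 5%.

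| Assumed event rate | R² | Effective n per arm | Power unadjusted | Power adjusted |
|---|---|---|---|---|
| 30% | 0.027–0.169 | 329–385 | 83.3% | 84.3–89.5% |
| 20% | 0.021–0.140 | 327–372 | 61.9% | 62.8–68.5% |
| 10% | 0.012–0.093 | 324–353 | 33.2% | 33.5–36.0% |
| 5% | 0.006–0.056 | 322–339 | 18.3% | 18.3–19.1% |
| 2% | 0.003–0.026 | 321–329 | 9.7% | 9.7–9.8% |

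Example at 20% and AUC 0.75: 320/(1−0.140) = 372. In interval width, the best case in the table is √(1−0.169) = 0.912, about 9% narrower. The weakest case at a 20% rate is √(1−0.021) = 0.99, about 1% narrower. R² is evaluated at the higher of the two arm rates, so the adjusted power figures are slightly generous.

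**Step 3: simulation check.** 640 women, 1,500 replicates per setting, one prognostic score (log-odds 0.36, 0.75 or 1.0 per standard deviation) and an arm odds ratio of 0.6. Adjusted-to-unadjusted variance ratios were:

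- rate 25% in the reference arm: 0.976, 0.917, 0.893;
- rate 10% in the reference arm: 1.001, 0.955, 0.937.

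A separate simulation of caesarean section at about 25% (600 trials per setting, two covariates) gave unadjusted-to-adjusted ratios of 1.02, 1.07 and 1.15 at R² of 0.035, 0.072 and 0.118. Inverting the first 25% series gives 1/0.976 = 1.02, 1/0.917 = 1.09 and 1/0.893 = 1.12. Both simulations point to a gain worth roughly 2% to 15% more women for a common outcome.

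**Step 4: which variables qualify.** An adjuster must precede allocation.

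- Demographics and medical history are recorded for every recruited woman. Age is a natural candidate. BMI is not named in the documents.
- Biometry at 19-21 weeks is described under Study protocol as part of what women randomised to each protocol receive, and recruitment is offered at that same scan. The text does not show that the measurement precedes allocation.
- Uterine Doppler at 19-21 weeks is specified only for the longitudinal arm, and third-trimester ultrasound follows randomisation. Neither can serve.

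**The case against.** The strongest case against is that nothing here is a defect. Unadjusted tests in a randomised trial analysed by intention to treat are valid, and the primary outcome and the 704 are untouched. That stands in full.

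The size is also assumed throughout, and the upper end may be optimistic. Entry is limited to nulliparous women with singletons, and several risk conditions are excluded, so parity cannot contribute. Women with abnormal 19-21 week biometry are excluded from further analysis, which truncates the range of that variable even if it could be used. This is a fair reason to expect the lower or middle part of the range.

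For the mild composite, moving power from 33.2% to at most 36.0% at a 10% rate does not rescue an outcome that has no sample size of its own. That also stands, and is why adjustment there is optional.

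A reader might infer more than the documents support:

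- *The baseline data serve description alone.* They do not; a randomisation check and a comparison with non-recruited women are also stated.
- *The unadjusted results would be biased.* Randomisation protects them.
- *Adjustment removes chance imbalance.* It deals only with the covariates in the model.
- *All the covariates needed are already in hand.* BMI and the timing of 19-21 week biometry are unconfirmed.

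What survives is narrower: a modest gain for a common outcome, at almost no cost.

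**Conclusion.** The point holds as a minor efficiency improvement for secondary outcomes. The variance of the risk difference would fall by about 2% to 17% at event rates of 20% to 30%, by about 1% to 9% at 10%, and by under 3% at 2%. At a 2% rate only about 0.02 × 640 ≈ 13 events would be expected, too few to carry a covariate list, so the severe composite should not be adjusted.

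These figures rest on assumed event rates, an assumed covariate AUC of 0.60 to 0.75, and 320 evaluable women per arm. The contribution of centre was not quantified. The gain applies to a marginal measure such as the standardised risk difference; the standard error of an adjusted odds ratio, which is a conditional quantity, need not shrink.

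**What to change.** Add one paragraph to STATISTICS, for secondary outcomes only and fixed before outcome data are seen:

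- For caesarean section, and optionally the mild composite, fit a logistic model with arm, centre (small centres pooled) and a short fixed list of pre-randomisation maternal variables on the CRF, such as maternal age, and BMI if the sponsor confirms it is recorded. Do not choose covariates by balance tests.
- Report the standardised risk difference with a robust or bootstrap 95% confidence interval, and keep the chi-square or Fisher test as a check.
- Use 19-21 week biometry only if it is confirmed to be measured before allocation. Do not adjust for uterine Doppler or third-trimester ultrasound variables.
- State how missing covariate values are handled, so that no randomised woman is lost from the model.

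Leave the primary sensitivity comparison, the severe composite, multi-category mode of delivery (which a binary model does not fit) and the 704 unchanged. The cost is plan wording, a slightly more complex analysis and a check of what the CRF holds. No new data are needed if the list keeps to variables already recorded.

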- **Single Scan at 28-32 weeks:** if **AC biometry and/or fetal weight is abnormal <10th, or crossed 50th centile from mid-trimester (screen positive)** further management will be performed according to local protocols.

All suspected fetal anomalies will be excluded from further analysis.

Women randomized to the **Longitudinal Scan Protocol**, besides the fetal anatomy screening, will receive a package of anatomy and biometric screening and Doppler interrogation of the Uterine arteries at 19-21 weeks of gestation and at 28-32 and 35-37 according to the following criteria:

- **Longitudinal Scan Protocol at 19-21 weeks:** if both **AC biometry and/or fetal weight** a biometric scan is scheduled at 28-32 weeks of gestation regardless the result of the Uterine Artery Doppler investigation. If **AC biometry and/or fetal weight are abnormal the case is excluded** from further analysis for third trimester screening, and the patient is then monitored according to local protocol
- **Longitudinal Scan Protocol at 28-32 weeks:** a standard package of fetal biometry, Amniotic Fluid index and Doppler interrogation of the Uterine arteries, Umbilical artery and Middle cerebral artery will be performed. If the **AC biometry and/or fetal weight** are normal, another biometric scan will be scheduled at 35-37 weeks of gestation and monitored until delivery according to local protocols (**screen negative**).
- **Longitudinal Scan Protocol at 35-37 weeks:** a standard package of fetal biometry, Amniotic Fluid index and Doppler interrogation of the Uterine arteries, Umbilical artery and Middle cerebral artery will be performed. If **AC biometry and/or fetal weight is abnormal <10th, or crossed 50th centile from mid-trimester (screen positive)** further management will be performed according to local protocols.

All scans after the dating scan in the first trimester are performed with mid-high quality ultrasound units. All ultrasound measurements follow the same protocols as those used in the clinical service, i.e. measurement of fetal head circumference, abdominal circumference, and femur length, using standard techniques.

Images produced to obtain recorded measurements are stored on digital media.

Attending clinicians are informed of the results obtained both by the Single Scan and by the Longitudinal Scan Protocols and will act according to local protocols when a diagnosis of IUGR is the result of the scan.

Measurements of outcome

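### Newborn weight is related to the ultrasound variables only through the <10th centile cut; a linear regression of the birth-weight z-score should be added beside the logistic model, not in its place

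*Combined protocol and SAP*

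**What the plan says.** The STATISTICS section of the combined protocol and SAP states that "Logistic regression models will be used to determine the magnitude of the association between ultrasound variables and newborn’s weight" below the 10th centile, and neonatal outcome. It lists no ultrasound variables, does not say whether they enter one at a time or together, and describes no regression of weight, centile or z-score as a continuous outcome. The significance rule is "A p value <0.05 will be considered statistically significant".

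The main outcome "is measured based Intergrowth21th newborn weight charts centiles" below the 10th, by sex. Classifying a newborn this way already needs what a z-score needs: birth weight, sex and gestational age.

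Under Study protocol, the Longitudinal arm's entries for 28-32 and for 35-37 weeks both say that "a standard package of fetal biometry, Amniotic Fluid index and Doppler interrogation of the Uterine arteries, Umbilical artery and Middle cerebral artery will be performed". It also has uterine artery Doppler at 19-21 weeks. The Single Scan arm has anatomy and biometry at 19-21 weeks and biometry at 28-32 weeks.

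For sample size, "each arm should comprise 32 subjects, which implies 64 for two arms". These are SGA births; the plan multiplies 64 by 10 to reach 640 women, and adds 10% to reach 704.

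**The concern.** The stated aim of the regression is the size of an association, which is an estimation question separate from the comparison of screening performance. Reducing every newborn to below or not below the 10th centile treats a baby at the 11th centile like one at the 90th. For a variable graded with fetal size, that discards usable information, and the events are fewest for the Doppler and fluid measurements that only the Longitudinal arm adds. The Background credits late screening particularly when combined with uterine Doppler, so readers will look to this analysis for what Doppler contributes. A non-significant odds ratio from about 32 events could be taken as evidence that a marker is unrelated to newborn size when the analysis had little chance of showing it.

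**Working it through.** **Inputs from the plan (STATISTICS).** Sensitivities 22.5% and 57%; 80% power; 5% significance, taken as two-sided because the plan does not say; 32 SGA births per arm; SGA proportion 10%, implied by 64 x 10 = 640.

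**1. The plan's own figure.** With mean proportion 0.3975, the two-proportion formula without continuity correction is [1.96 x sqrt(2 x 0.3975 x 0.6025) + 0.8416 x sqrt(0.225 x 0.775 + 0.57 x 0.43)]^2 / 0.345^2 = (1.3565 + 0.5451)^2 / 0.1190 = 30.4, so 31 per arm against the stated 32 (36 with the correction). Then 64 x 10 = 640 and 640 x 1.10 = 704. The figure is close enough to take 32 SGA births among 320 women per arm as the planning basis.

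**2. Events by variable.** Biometry at 19-21 and 28-32 weeks is measured in both arms: 640 women, about 64 SGA births. Protocol Doppler, fluid index and everything at 35-37 weeks are in the Longitudinal arm only: 320 women, about 32 SGA births (about 35 if all 352 are followed). The 35-37 week scan is scheduled where 28-32 week biometry is normal. If 22.5% of SGA cases screen positive earlier and are not rescanned under protocol (an assumption), 32 x 0.775 = about 25 remain.

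**3. Information kept by the cut, if the relation is linear.** For a normal outcome and a weak linear effect, relative efficiency is phi(z)^2 / [p(1-p)]. At p = 0.10: 0.1755^2 / 0.09 = 0.342. So 320 women count as 320 x 0.342 = about 110, and 640 as about 219. If the SGA proportion is 8%, 12% or 15% (assumed range), the loss is 70%, 62% or 57%.

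**4. Power, if the relation is linear.** Continuous outcome: Phi[sqrt(n) x r / sqrt(1 - r^2) - 1.96]. Cut: Phi[sqrt(0.342n) x r - 1.96]. The correlations are assumed; the plan gives none.

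| n | r | <10th cut | z-score |
|---|---|---|---|
| 320 | 0.10 | 18% | 44% |
| 320 | 0.15 | 35% | 77% |
| 320 | 0.20 | 55% | 95% |
| 640 | 0.10 | 32% | 72% |
| 640 | 0.15 | 60% | 97% |

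Simulation agrees (n = 320, r = 0.15: 34-36% logistic, 76-77% linear). The smallest correlation detectable with 80% power is 2.8016/sqrt(320) = 0.16 on the z-score and 2.8016/sqrt(110) = 0.27 with the cut; for 640 women, 0.11 and 0.19. At r = 0.40, simulated logistic power with 320 women is already 99%.

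**5. The opposite case: a marker that shifts only in SGA babies.** Assume a shift of 0.5 SD below the 10th centile and none elsewhere, with n = 320.
- Logistic: the true log odds ratio per SD is 0.50. Power is about Phi[0.5 x sqrt(320 x 0.09) - 1.96] = Phi(0.72) = 76%.
- Linear: the covariance with the z-score is 0.5 x 0.1755 = 0.0877 in size and the marker variance is 1 + 0.25 x 0.09 = 1.0225, so r = 0.087. Power is Phi[17.89 x 0.087 / 0.996 - 1.96] = about 34%.
- Odds ratio derived from the linear fit: the slope is 0.0877/1.0225 = 0.0858, and the implied log odds ratio is (0.1755/0.09) x 0.0858 = 0.17. That is an odds ratio of about 1.18, where the true one is 1.65.

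Simulation gives 75% logistic against 33% linear. For an intermediate case, a marker rising only below the 25th centile, simulation gives 79% against 59%.

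**The case against.** The target condition is SGA below the 10th centile, and logistic regression estimates association with it directly; a linear model answers a question about mean weight. The Background also describes Doppler changes as an adaptation of growth-restricted fetuses, which suggests a lower-tail effect more than a gradient across normal weights. Step 5 shows that the logistic model is then the more powerful one. All of this stands. It is why the logistic model should stay, and why its odds ratio should not be replaced by one derived from the linear fit.

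A reader might go further and infer that the planned model always discards two thirds of the information. The documents do not support that: the figure needs a linear relation over the whole weight range, which they nowhere state.

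A reader might also count the scan variables against 32 events and infer overfitting and inflated odds ratios. That does not follow either. The plan speaks of models in the plural and specifies no joint model, variable list or selection step.

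Finally, the analysis is not a listed outcome, does not drive the sample size, and is not the only look at discrimination, since ROC areas with confidence intervals are also planned. That limits the weight of the point. It does not remove the case for a supplementary model that needs no new data.

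**Conclusion.** The point holds as a minor improvement to a supporting analysis. The plan relates ultrasound variables to newborn weight only through the 10th-centile cut, on about 64 SGA births for biometry common to both arms and about 32 for Longitudinal-only measurements. Under a roughly linear relation and a 10% SGA proportion, the cut keeps about 34% of the information, and weak to moderate predictors (correlations of about 0.10 to 0.20, an assumed range) would often be missed. Strong predictors would not. Under a tail-only relation the advantage passes to the logistic model. The documents do not settle which pattern applies to which variable, so neither model suffices alone, and a weak or null logistic result is not evidence of no association. The primary sensitivity comparison, for which the <10th cut is the screening target, is not in question.

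**What to change.** In STATISTICS, keep the logistic model as the direct estimate of association with birth weight below the 10th centile. Add a sentence pre-specifying a linear regression of the Intergrowth birth-weight z-score on the same ultrasound variables, kept continuous, reported beside the logistic results, with a check of non-linearity such as a spline term. State that the two are interpreted together and that a non-significant odds ratio will not be reported as absence of association. Do not derive the <10th centile odds ratio from the linear model: it is biased towards no effect when the association is confined to the lower tail.

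The cost is a sentence or two of text and one extra model, with no new data, visits or participants. The downside is two sets of results that may differ and need joint interpretation; a difference would itself suggest whether a marker follows size in general or mainly the smallest babies.
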